**Table 4: Dose escalation/de-escalation rule for the Boin design**

[figure not shown]
Number of subjects treated at current dose	3	4	5	6	7	8	9
Escalate if number of DLTs is less than or equal to	0	0	0	0	1	1	1
De-escalate if number of DLTs equal to or greater than	1*	1*	2	2	2	2	3
Eliminate if number of DLTs equal to or greater than	2	3	3	3	4	4	4

Note. # of DLT is the number of subjects with at least 1 DLT in the first 28 days of dosing. Observations from IPDE will not be considered (Section 6.9). When none of the actions (i.e., escalate, de-escalate or eliminate) is triggered, stay at the current dose for treating the next cohort of subjects. \*The SRC can decide to enroll an additional 3 subjects at this dose level. In case the multiple dosing regimens are initiated simultaneously and parallel enrollment is allowed in the multiple dosing regimens, the evaluation for Boin rule for each dose level and regimen would be made separately.

In [Table 4](#), if 1 out of 3 or 4 subjects experience a DLT in the first cycle of treatment, the algorithm recommends dose de-escalation, rather than staying at the current dose. Considering only information from 3 to 4 subjects will be initially available, the incidence of 1 DLT does not sufficiently establish that the MTD is exceeded. Under this situation, a recently published i3+3 design recommends staying in the current dose level if the observed number of DLTs is only 1 greater than the number required for dose escalation. Therefore, the Safety Review Committee could decide to enroll an additional 3 subjects at that dose level, if only 1 of 3 or 4 subjects experiences a DLT.

Formatted: C-[Hyperlink](#)

**Figure 2: Flowchart for Trial Conduct Using the BOIN Design**

After the trial is completed, select the MTD based on isotonic regression as specified in Liu and Yuan (2015). This computation is implemented by the ‘Shiny App’ ‘BOIN’ available at <http://www.trialdesign.org>. Specifically, select as the MTD the dose for which the isotonic estimate of the toxicity rate is closest to the target toxicity rate. If there are ties, select the higher dose level when the isotonic estimate is lower than the target toxicity rate and select the lower dose level when the isotonic estimate is greater than or equal to the target toxicity rate.

Up to approximately 18 additional subjects (no more than 9 additional subjects per dose) will be enrolled at a safe dose(s) below or at the MTD for additional experience with safety and efficacy. We will use the elimination boundaries in [Table 4](#) for the toxicity monitoring.

The RP2D will be recommended by the SRC based on efficacy, safety and PK/PD data evaluation and may or may not be the same dose as the determined MTD dose.

Formatted: C-Hyperlink

### 3.2.1. Operation Characteristics for BOIN Design

[Table 5](#) shows the operating characteristics of the trial design based on 1000 simulations of the trial using shiny app ‘BOIN’ available at <http://www.trialdesign.org>. The operating characteristics show that the design selects the true MTD, if any, with high probability and allocates more subjects to the dose levels with the DLT rate closest to the target of 0.2.

Formatted: C-Hyperlink

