### 3.2. Phase 1 Design

The primary objective of Phase 1 is to determine the Maximum Tolerated Dose (MTD) and the Recommended Phase 2 Dose (RP2D) of DS-1594b when administered as a single agent in subjects with relapsed or refractory AML or ALL, including subjects with or without MLLr or NPM1m using a Bayesian optimal interval (BOIN) design to find the MTD.

The BOIN design is implemented in a simple way similar to the traditional 3+3 design but is more flexible and possesses superior operating characteristics that are comparable to those of the more complex model-based designs, such as the continual reassessment method (CRM).

At least 3 subjects must be enrolled at each dose level. If a dose level is found to be safe by the BOIN design we will escalate to the next higher dose level. The SRC can recommend additional enrollment of up to 9 additional subjects per dose level for dose levels that have already been deemed to be safe with the intent to gain additional information on safety, efficacy and PK at different dose levels, and to guide selection of optimal biologically effective RP2D. These additional 9 subjects per dose level will not be considered evaluable for DLTs. It is anticipated that approximately 18 subjects will be added in this Phase 1 expansion.

Although all R/R ALL and R/R AML subjects, irrespective of mutations, will be allowed during the Phase 1 dose-escalation the goal is to treat at least 3 subjects with MLLr or NPM1m are included at dose levels that are anticipated to be biologically active to allow for optimal evaluation of safety and efficacy in the presumed target population to guide selection of the optimal RP2D.

Treatment during Phase 1 dose escalation phase will follow continuous oral administration under a twice-daily schedule or daily schedule on a 28-day dosing cycle.

The first dose cohort will start at 70 mg twice daily, approximately every 12 hours. The target toxicity rate for the MTD is  $\phi = 0.2$  and the maximum sample size for determining the MTD is 42. Each cohort will include a minimum of 3 subjects. The DLT evaluation period will be limited to the first 28 days of dosing. DLTs are defined in Section 3.2.2 and only those DLTs that occur within the first cycle (28 days) will be used for dose finding. As shown in [Figure 2](#), the BOIN design uses the following rule, optimized to minimize the probability of incorrect dose assignment, to guide dose escalation/de-escalation:

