Formatted: C-Hyperlink

- if the observed DLT rate at the current dose is 0.157 or less, escalate the dose to the next higher dose level;
- if the observed DLT rate at the current dose is more than 0.238, de-escalate the dose to the next lower dose level;
- otherwise, stay at the current dose.

Evaluation by the abovementioned BOIN rule will be done for each dose level separately based on the cumulative number of DLT evaluable subjects treated in that dose level and regimen (i.e., QD or BID). In case the multiple dosing regimens are initiated simultaneously and parallel enrollment is allowed in the multiple dosing regimens, the evaluation by the BOIN rule for each dose level and regimen would be made separately. DLT observed after intra-patient dose escalation (IPDE) will not be considered in the dose escalation/de-escalation decision (See Section 6.9 for details about IPDE). For the purpose of overdose control, doses  $j$  and higher levels will be eliminated from further examination if  $\Pr(p_j > 0.2 | \text{data}) > 0.95$  and at least 3 subjects have been treated at dose level  $j$ , where  $p_j$  is the true DLT rate of dose level  $j$ ,  $j = 1, \dots, 6$ . This posterior probability is evaluated based on the beta-binomial model  $y_j | p_j \sim \text{binomial}(p_j)$  with  $p_j \sim \text{uniform}(0,1)$ , where  $y_j$  is the number of subjects who experienced DLT at dose level  $j$ . When the lowest dose is eliminated, stop the trial for safety. The probability cutoff 0.95 is chosen to be consistent with the common practice that when the target DLT rate  $\leq 1/6$ , a dose with 2/3 subjects experienced DLT is eliminated. The above dose escalation/de-escalation and elimination rule can be equivalently presented in [Table 4](#), which will be used to conduct the trial.

Formatted: C-Hyperlink

The steps to implement the BOIN design are described as follows:

1. Three subjects in the first cohort are treated at dose level 1 (70 mg twice daily). Each cohort will include a minimum of 3 subjects.
2. To assign a dose to the next cohort of subjects, conduct dose escalation/de-escalation according to the rule displayed in [Table 4](#). When using [Table 4](#), please note the following:
  - a. “Eliminate” means eliminate the current and higher doses from the trial to prevent treating any future subjects at these doses because they are overly toxic.

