  - b. When we eliminate a dose, automatically de-escalate the dose to the next lower level. When the lowest dose is eliminated, stop the trial for safety. In this case, no dose should be selected as the MTD.
  - c. If none of the actions (i.e., escalation, de-escalation or elimination) is triggered, treat the new subjects at the current dose.
  - d. If the current dose is the lowest dose and the rule indicates dose de-escalation, treat the new subjects at the lowest dose unless the number of DLTs reaches the elimination boundary, at which point terminate the trial for safety.
  - e. If the current dose is the highest dose and the rule indicates dose escalation, treat the new subjects at the highest dose.

Formatted: C-Hyperlink

Formatted: C-Hyperlink

3. Repeat step 3 until the maximum sample size of 30 is reached or stop the trial if the number of subjects treated at the current dose reaches 9 and the decision according to [Table 4](#) is to stay at the current dose.

Formatted: C-[Hyperlink](#)

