### **9.1. Phase 1**

The primary objective of Phase 1 is to determine the MTD and RP2D of DS-1594b when administered as a single agent in subjects with R/R AML or R/R ALL, including subjects with or without MLLr or NPM1m using a Bayesian optimal interval (BOIN) design (Liu and Yuan, 2015; Yuan et al., 2016) to find the MTD. The details of the BOIN design to be used in the Phase 1 are outlined in Section 3.2.

According to the BOIN design, cohorts of 3 subjects will be treated at each dose level. If a dose level is found to be safe by the BOIN design we will escalate to the next higher dose level. Evaluation for above mentioned BOIN rule will be done for each dose level and dosing regimen (i.e., QD vs BID) separately based on the cumulative number of DLT evaluable subjects treated in that dose level. In case the multiple dosing regimens are initiated simultaneously and parallel enrollment is allowed in the multiple dosing regimens, the evaluation for BOIN rule for each dose level and dosing regimen would be made separately. Up to 9 additional subjects may be enrolled at each dose level that has already been deemed to be safe with the intent to gain additional information on safety and efficacy at different dose levels, to guide selection of optimal biologically effective RP2D. Although all R/R ALL and R/R AML subjects, irrespective of mutations, will be allowed during the Phase 1 dose-escalation it is suggested that at least 3 subjects with MLLr or NPM1m are included at each dose level that is anticipated to be clinically active, to allow for optimal evaluation of safety and efficacy in the presumed target population to guide selection of the optimal RP2D. As described in Section 3.2, we will use the same the elimination boundaries in Table 4 for the toxicity monitoring in the expansion cohort(s).

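### Table 5 cannot come from the written cohorts-of-3 BOIN rules, and the dose-finding cap is given as both 42 and 30

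*Combined protocol and SAP*

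**What the plan says.** Section 3.2 fixes how dose finding starts and proceeds. Step 1 of the algorithm reads "Three subjects in the first cohort are treated at dose level 1 (70 mg twice daily"), and the general rule is "At least 3 subjects must be enrolled at each dose level". Section 9.1 repeats that "cohorts of 3 subjects will be treated at each dose level". Escalation is at an observed DLT rate of 0.157 or less and de-escalation above 0.238. Table 4 gives the elimination counts. Dose finding ends early when 9 subjects are at the current dose and the decision is to stay.

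The overall limit appears twice with different values. The text of Section 3.2 says "the maximum sample size for determining the MTD is 42", and Section 9 also uses 42. Step 3 of the algorithm says "Repeat step 3 until the maximum sample size of 30 is reached".

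Section 3.2.1 presents Table 5 as the result of 1000 simulations of this design and concludes: "The operating characteristics show that the design selects the true MTD, if any, with high probability". It adds that more subjects go to the dose levels with the "DLT rate closest to the target of 0.2".

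**The concern.** Two features of Table 5 look incompatible with cohorts of 3. The percentages treated at dose 1 in Scenarios 3 to 6 (5.4% to 8.4%) are too small for trials averaging about 20 to 24 subjects. Scenario 1, where doses 4 to 6 have true DLT rates of 45% to 55%, still puts 8 + 4.4 + 2 = 14.4% of subjects on those doses, although cohorts of 3 should rarely climb that far.

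Table 5 is the only trial-specific evidence for the accuracy of MTD selection in a first-in-human study whose MTD informs the Phase 2 dose for four cohorts. If it describes a different algorithm, readers have been shown the wrong accuracy and the wrong expected sample size. Separately, with two caps, the point at which dose-finding enrolment must end is ambiguous whenever neither early-stopping rule has applied.

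**Working it through.** **Inputs.** True DLT rates, selection percentages, patient shares and mean N come from Table 5. The decision boundaries and the stop at 9 with a stay decision come from Section 3.2, the elimination rule (uniform prior, cutoff 0.95) from Section 3.2 and Table 4, and isotonic MTD selection from the text after Figure 2. The target is 0.2.

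**Step 1: reproduce Table 4.** These boundaries and the elimination rule regenerate every cell, including the elimination row 2, 3, 3, 3, 4, 4, 4 for n = 3 to 9. The coded rules are therefore the plan's rules.

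**Step 2: subjects at dose 1 implied by Table 5.** Mean at dose 1 = dose-1 share × mean N.

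| Scenario | Share × mean N | Implied mean |
|---|---|---|
| 1 | 41.4% × 18.2 | 7.53 |
| 2 | 24.5% × 22 | 5.39 |
| 3 | 8.4% × 23.7 | 1.99 |
| 4 | 6.2% × 23.6 | 1.46 |
| 5 | 5.4% × 22.9 | 1.24 |
| 6 | 6.6% × 19.7 | 1.30 |

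No trial can have fewer than 3 at dose 1, so no average can. Scenarios 3 to 6 are impossible, and this needs no simulation.

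**Step 3: the other reading of the share.** If the column is instead the average of per-trial percentages, its floor is 3/30 = 10% with the cap of 30, or 3/42 = 7.1% with 42. All four scenarios break the first floor. Scenarios 4 to 6 also break the second.

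**Step 4: simulate the written rules.** Cohorts of 3, stop at 9 with stay, 10,000 trials per scenario. An instruction to escalate at the top dose or de-escalate at the lowest is treated as stay.

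| Scenario | Correct selection %: Table 5 / cap 30 / cap 42 | Mean N: Table 5 / cap 30 / cap 42 | Dose-1 share %: Table 5 / cap 30 |
|---|---|---|---|
| 1 | 57.5 / 64.0 / 64.5 | 18.2 / 13.4 / 13.8 | 41.4 / 62.3 |
| 2 | 47.4 / 49.7 / 50.7 | 22 / 18.8 / 19.8 | 24.5 / 38.5 |
| 3 | 56.4 / 52.7 / 54.4 | 23.7 / 22.6 / 24.1 | 8.4 / 19.2 |
| 4 | 54.9 / 47.8 / 50.8 | 23.6 / 24.6 / 26.9 | 6.2 / 15.0 |
| 5 | 49.5 / 39.7 / 45.0 | 22.9 / 26.2 / 29.0 | 5.4 / 13.7 |
| 6 | 64.4 / 45.6 / 49.3 | 19.7 / 26.3 / 29.2 | 6.6 / 14.3 |

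Scenario 1 early stopping at cap 30 is 17.2% (Table 5: 13.2%). The share on doses 4 to 6 there is about 1.5% to 1.8% (Table 5: 14.4%). The Monte Carlo standard error of 64.4% from 1000 trials is √(0.644 × 0.356 / 1000) = 1.5 points. The smaller Scenario 6 gap, 64.4 − 49.3 = 15.1 points, is about ten times that. Separate codings of the same rules put Scenario 6 at 40.9% to 46.4% (cap 30) and 47.9% to 49.4% (cap 42), so the direction is firm but not the last digit.

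**Step 5: variants within cohorts of 3.** If the Safety Review Committee always uses its option to add 3 subjects after 1 DLT in 3 or 4, Scenario 6 selection is 51.9% to 53.8% and the dose-1 share 12.5% to 13.4%. Across all cohorts-of-3 variants, including other readings of the stop at 9, the dose-1 share is never below 11.8%. In Scenario 6, selection never exceeds 53.8% and mean N is never below 20.9.

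**Step 6: what does resemble Table 5.** Single-patient escalation to the first DLT, then cohorts of 3, with a cap of 30, gives mean N of 18.4 / 21.9 / 23.3 / 23.6 / 22.5 / 19.8. Patient shares fall within 1.8 points of Table 5 and correct selection within 3.5. The plan contains no such rule. Section 9 uses the word titration as a label for the BOIN stage but defines no single-patient step.

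**The case against.** The strongest reply is about balance and consequence.

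- **The written rules are not uniformly worse.** They do better in Scenarios 1 and 2 and are more cautious. In Scenario 1 about 38% to 39% of subjects are treated above the MTD, against 29.8 + 14.4 + 8 + 4.4 + 2 = 58.6% in Table 5. The error does not conceal a safety risk. This stands.
- **Table 4 governs conduct, and it is correct.** The doses after the first are tentative, and the committee may choose a Phase 2 dose other than the MTD. This stands too: apart from the cap, correcting Table 5 changes no dosing decision.
- **Planned enrolment does not rest on Table 5's mean N.** True. The simulated means all fit within either cap, so no enrolment figure is shown to be wrong beyond the 30/42 conflict. The 9-and-stay and elimination stops remain defined; only the cap is ambiguous.
- **Section 3.2 cites a comparative review for BOIN's performance.** That support is generic. It says nothing about these six scenarios.
- **The single-patient explanation is an inference.** Correct. Under it, Scenario 1 early stopping is 11.2% against 13.2%, and cohorts of 1 match the shares within 1.1 points, though they fit mean N less well (16.1, 19.7 and 21.2 against 18.2, 22 and 23.7 in Scenarios 1 to 3).

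None of this touches Step 2.

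**Conclusion.** The plan is wrong as written on both counts. Table 5 is not the table of the written design: four of its six scenarios imply fewer than 3 subjects at dose 1, which the rules forbid. That conclusion rests only on the table's own figures and the minimum of 3.

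The size of the error rests on simulation with the stated coding choices. Correct selection is understated in Scenarios 1 and 2 and overstated in Scenarios 3 to 6, most in Scenario 6 by 15.1 to 18.8 points (64.4 minus 49.3 or 45.6). Scenario 6 also needs 6.6 to 9.5 more subjects on average than stated. Under the written rules correct selection runs from 39.7% to 64.0% at cap 30 and from 45.0% to 64.5% at cap 42, which does not support an unqualified claim of high probability. Why Table 5 differs is not established; a single-patient run-in is the likeliest explanation. The conflict between 42 and 30 is explicit.

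**What to change.** 1. State one maximum sample size for dose finding, identical in the text of Section 3.2, in step 3 of the algorithm and in Section 9.
2. Re-run Table 5 with cohorts of 3, that cap and the stop at 9 with stay, once with and once without the committee's option to add 3 subjects. State how an instruction to escalate at the top dose is treated for the stop at 9.
3. Check the new table before issue: dose-1 share × mean N must be at least 3 in every scenario.
4. Rewrite the accuracy sentence in Section 3.2.1 to report the range obtained.
5. If a single-patient run-in was intended, the algorithm in Section 3.2 and Table 5 must be reconciled. This note takes no position on which should stand.

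The cost is about an hour of simulation and a wording amendment, with no additional patients. The reported accuracy will look worse in Scenarios 3 to 6 and better in Scenarios 1 and 2.

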**Table 5: Operating Characteristics of the Boin Design**

Dose	1	2	3	4	5	6	Number of Subjects	% Early Stopping
Scenario 1								
True DLT Rate	0.2	0.34	0.4	0.45	0.5	0.55		
Selection %	57.5	20.9	4.9	2.4	1	0.1		13.2
% Pts Treated	41.4	29.8	14.4	8	4.4	2	18.2	
Scenario 2								
True DLT Rate	0.09	0.2	0.35	0.41	0.48	0.54		
Selection %	24.1	47.4	19.2	5.5	1	0.5		2.3
% Pts Treated	24.5	33.5	22.4	11.6	5.8	2.3	22	
Scenario 3								
True DLT Rate	0.02	0.08	0.2	0.37	0.43	0.49		
Selection %	1.5	22	56.4	16.4	2.6	1.1		0
% Pts Treated	8.4	22.4	33.8	21.4	9.6	4.4	23.7	
Scenario 4								
True DLT Rate	0.01	0.05	0.09	0.2	0.38	0.51		
Selection %	1	4.2	22.8	54.9	14.7	2.3		0.1
% Pts Treated	6.2	10.2	22.1	32.4	21.1	7.9	23.6	
Scenario 5								
True DLT Rate	0.01	0.04	0.07	0.1	0.2	0.37		
Selection %	0.2	1.4	6.6	23.1	49.5	19.2		0
% Pts Treated	5.4	7.9	12.3	22.8	31.9	19.8	22.9	
Scenario 6								
True DLT Rate	0.02	0.04	0.06	0.08	0.1	0.2		
Selection %	0.1	2	4	6.1	23.3	64.4		0.1
% Pts Treated	6.6	8.6	11	13.9	23.9	35.9	19.7	

Note: “% Early Stopping” refers to early stopping due to excessive DLT.

The SRC will meet when there are a sufficient number of DLT-evaluable subjects to review in the current cohort who have completed the Cycle 1, 28-day DLT evaluation period, and before proceeding to the next cohort at a higher dose level.

The dose-escalation recommendation obtained via the Boin design will be reviewed by the SRC, along with the DLT data, other AE data, and available PK/PD and laboratory data before implementation of the next dose cohort.

If a lower dose is recommended by the Boin method and confirmed by the SRC, then enrollment into the next lower dose level may be initiated, and additional cohorts may be opened to enroll subjects into a previously tested safe dose level to facilitate the evaluation of the dose-toxicity relationship.

### 3.2.2. Dose-Limiting Toxicity Definition

Dose-Limiting Toxicity (DLT) is defined in this study as a non-hematologic adverse event or abnormal laboratory value assessed as unrelated to disease progression, intercurrent illness, or concomitant medications and occurring during the first 28 days on study that meets any of the following criteria, using the Common Terminology Criteria for Adverse Events (CTCAE) grading system, version 5.0:

- Hematologic DLT is defined as CTCAE Grade 4 neutropenia (absolute neutrophil count  $<0.5 \times 10^9 /L$ ) or thrombocytopenia (platelet count  $<25.0 \times 10^9 /L$ ) lasting for 42 days or more from Cycle 1 Day 1 in the absence of residual leukemia (i.e., with less than 5% blasts by morphology or residual leukemia by flow-cytometry).
  - Anemia will not be considered for the definition of DLT.
- CTCAE Grade 3 AST (SGOT) or ALT (SGPT) increased for at least 7 days or Grade 3 hyperbilirubinemia for at least 7 days.
- CTCAE Grade 3 AST (SGOT) or ALT (SGPT) increased accompanied by Grade 2 bilirubin increase
- CTCAE Grade 4 AST (SGOT) or ALT (SGPT) increased of any duration
- Any other non-hematological adverse events that are CTCAE Grade 3 or 4. However, the following adverse events are NOT considered DLTs:
  - Grade 3 nausea, vomiting and diarrhea will be considered DLT only if not controlled to Grade 2 or lower with optimal therapy within 72 hours (not including tube feeding, total parenteral nutrition, and/or hospitalization). Any Grade 3 gastrointestinal toxicity requiring tube feeding, total parenteral nutrition, and/or hospitalization and any Grade 4 gastrointestinal toxicity will be considered DLT.
  - Grade 3 or 4 biochemical abnormalities (e.g., lipase or amylase increased) will only be considered DLT if accompanied by clinical consequences.
  - Grade 3 or 4 isolated electrolyte abnormalities must be without clinical consequence and resolve, with or without intervention, to less than Grade 2 levels within 72 hours.
  - Grade 3 infusion reaction if successfully managed and which resolves within 72 hours
  - Grade 3 or 4 Tumor Lysis Syndrome if it is successfully managed clinically and resolves within 7 days without end-organ damage
  - Grade 3 or 4 Differentiation Syndrome which improves to  $\leq$  Grade 1 within 7 days of the start date of  $\geq$  Grade 3 Differentiation Syndrome and which is not associated with end-organ damage. Note: Grade 1 is mild, Grade 2 is moderate, Grade 3 is serious, and Grade 4 is life-threatening.

- CTCAE Grade 3 QTcF prolongation (based on the average of 3 triplicate 12-lead readings or Holter monitor reading)
- Results in dose-reduction or discontinuation of therapy
- Any treatment-related death;
- Subjects not considered evaluable due to insufficient dosing (at least 75% of doses of study drugs) and who do not develop a toxicity that is considered a DLT will be replaced. These subjects may continue therapy on trial after discussion with the Principal Investigator if they are having clinical benefit and the reasons for continuation and potential benefit/risk profile for the subject must be clearly documented in the medical records.
- **Phase 2 only:** For subjects in venetoclax- or Mini-HCVD-containing regimens (cohorts C and D) who do not receive venetoclax or Mini-HCVD on Day 1 due to logistical and/or financial reasons, the DLT period will be extended to 28 days from the first dose of venetoclax or Mini-HCVD. For evaluation of hematologic-related DLT, the DLT evaluation period will be 42 days from the first dose of venetoclax or Mini-HCVD.
- Subjects must receive at least 75% of the doses of DS-1594b, azacitidine (Phase 2 only), venetoclax (Phase 2 only), or miniHCVD (Phase 2) during the first 28 days on trial (i.e. during Cycle 1) to be considered evaluable during the DLT evaluation period. Subjects who receive less than these planned number of doses of each drug during the first 28 days on trial will not be considered evaluable during the DLT evaluation period. However, if such subjects develop a toxicity that would normally be considered a DLT this will still be captured as a DLT. Any toxicity that meets the criteria for DLT during the first 28 days of trial in a subject who has received at least one dose of trial medication will constitute a DLT.
- For subjects who discontinue therapy, the reason for treatment discontinuation will be documented.
- Dose modifications other than the ones mentioned above can be considered after discussion with the PI and proper documentation of the rationale.

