## 3.3. Phase 2 Design

Enrollment in Phase 2 will start once the RP2D has been determined in Phase 1. This Phase 2 study will have four cohorts:

- Cohort A: DS-1594b monotherapy for R/R AML with MLL-r,
- Cohort B: DS-1594b monotherapy for R/R AML with NPM1m,
- Cohort C: DS-1594b in combination with azacitidine and venetoclax for R/R AML with NPM1m or MLLr
- Cohort D: DS-1594b in combination of mini-HCVD for R/R ALL with MLLr

Subjects enrolled in Cohorts A and B will receive the RP2D dose of DS-1594b determined in Phase 1. Cohorts C and D will enroll an initial 6 subjects in a safety run-in at one dose level below the RP2D (Dose level 0) with DS-1594b dose titration as specified below.

Cohorts A and B (single agent cohorts) will enroll a maximum of 26 subjects, and Cohorts C and D (combination cohorts) will enroll a maximum of 32 subjects, to allow reasonable determination of CRc within 3 months of therapy initiation.

For the combination cohorts (C & D) there will be a safety-run in evaluation with pre-defined toxicity stopping rules to be implemented for early DLT evaluation as per following plan:

- Safety run-in evaluation by the Safety Review Committee of the first 6 subjects in cohorts C and D will occur after 6 subjects have completed at least one cycle of treatment (or at least 28 days from the first day of treatment).
- Enrollment will be paused while the first 6 subjects are evaluated for safety. Each combination cohort will be evaluated independently.
  - If  $\leq 1$  of the 6 subjects experiences DLT in the first cycle of treatment, the treatment combination will be considered as safe and the DS-1594b dose can be escalated to the RP2D (Dose level 1) for the treatment of the next 6 patients (repeat the safety run-in evaluation). If the RP2D (Dose level 1) is considered safe, continue enrollment of an additional 20 subjects at the RP2D (i.e. total subjects treated at the RP2D will be 26 subjects; total cohort size will be 32 subjects). If  $\geq 2$  of 6 subjects at the RP2D experiences DLT in the first cycle of treatment, de-escalate and continue enrollment of an additional 20 subjects at Dose Level 0.

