- If a bone marrow remission (< 5% blasts) or aplasia/hypoplasia is not noted on the Day 21 bone marrow, subjects should continue venetoclax until day 28 and have a repeat bone marrow on Day 28 (+/- 5 days). If the Day 28 bone marrow shows  $\geq 5\%$  blasts proceed with Cycle 2 if this is in the best interest of the subject (those with C1D28 bone marrow  $\geq 5\%$  are allowed to receive 21 days of venetoclax in Cycle 2 after discussion with and approval from the PI). If the Day 28 bone marrow shows < 5% blasts or aplasia/hypoplasia follow steps outlined in “a” and “b” above.
- Treatment interruptions and dosing schedules other than the ones mentioned above can be considered after discussion with the PI and proper documentation of the rationale.
- DS-1594b administration will continue as scheduled and will not be impacted or adjusted based on venetoclax dosing schema or venetoclax-related delays.
- Physicians should leukoreduce with hydroxyurea to reduce the peripheral white blood count to below  $10 \times 10^9/L$  prior to the administration of the first dose of venetoclax. If the WBC is more than  $10 \times 10^9/L$ , the venetoclax should not be initiated till the white count is brought down to below  $10 \times 10^9/L$ .
- The subject will be admitted to the hospital for at least the first 7 days of the 1st cycle of concomitant azacitidine-venetoclax-DS-1594b therapy (e.g., Day 1 through Day 7) of Cycle 1, potentially admission will be longer if we encounter TLS, infections or other complications that would be better managed in the in-patient setting. To mitigate the risk for tumor lysis syndrome, subjects must be receiving tumor lysis prophylaxis, including hydration (oral, intravenous) and treatment with a uric acid reducing agent (allopurinol, rasburicase) prior to the start of venetoclax therapy and continued during Cycle 1.

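### In Cohort C the 28-day DLT window restarts at first venetoclax for a logistical or financial delay but not for the protocol's own white-count deferral, so some run-in subjects are observed on the combination for up to 7 days less

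*Combined protocol and SAP*

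**What the plan says.** **Default window.** Section 3.2.2 counts events "occurring during the first 28 days on study that meets any of the following criteria". Its haematologic criterion is a cytopenia "lasting for 42 days or more from Cycle 1 Day 1 in the absence of residual leukemia".

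**Extension.** For Cohort C and D subjects "who do not receive venetoclax or Mini-HCVD on Day 1 due to logistical and/or financial reasons, the DLT period will be extended", with 28 days counted from the start of the missing drug. The next sentence says that for haematologic DLTs "the DLT evaluation period will be 42 days from the first dose of venetoclax or Mini-HCVD", and it does not repeat the reason for delay.

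**White-count deferral.** Section 5.4.1, under Azacitidine, says that above 10 x 10^9/L "the venetoclax should not be initiated till the white count is brought down to below" that level. It gives no maximum delay. The same section says that "DS-1594b administration will continue as scheduled and will not be impacted or adjusted based on venetoclax dosing schema or venetoclax-related delays". Section 5.4.2 counts Day 1 of each cycle from azacitidine.

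**Evaluability.** Sections 3.2.2 and 3.3 require at least 75% of doses, counted over the first 28 days of the trial. Section 3.3 replaces non-evaluable run-in subjects. Section 3.2.2 still counts a DLT in any subject who has had at least one dose.

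**Review and decision.** Section 3.3 says the run-in evaluation "will occur after 6 subjects have completed at least one cycle of treatment (or at least 28 days from the first day of treatment". Its last bullet has the Safety Review Committee (SRC) meet once enough evaluable subjects have completed the DLT evaluation period. At most 1 DLT in 6 clears the combination and allows DS-1594b to rise to the RP2D.

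**The concern.** The extension clause accepts that a subject who starts venetoclax late needs a window counted from that start. It then limits this to two administrative reasons and leaves out the one delay that the protocol itself imposes. Two subjects with the same 7-day delay are followed for different times after first venetoclax, according to the reason recorded.

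The run-in is the first test of DS-1594b in combination (Section 3.3.1), and the footnotes to Table 6 note that DS-1594b may inhibit the metabolism and transport of venetoclax. With six subjects and a cut between 1 and 2 DLTs, one late event that falls outside a shortened window can turn a failed run-in into a cleared one.

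The period for the 75% count also does not move with the extension, so the existing clause is at odds with the evaluability rule even for the delays it does cover.

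**Working it through.** **Inputs.** Planned Cycle 1 venetoclax is 28 daily doses (Table 6 footnotes). The evaluability floor is 75% of doses in Days 1 to 28, read as applying to each drug separately (Section 3.2.2). The default window ends on Day 28 and the default haematologic clock on Day 42 (Section 3.2.2).

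**The plan's own figure.** Section 9.4.1.3 gives 42 of 56 DS-1594b doses: 0.75 x 56 = 42, reproduced. The same rule for venetoclax gives 0.75 x 28 = 21 doses.

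**Delay arithmetic.** Let venetoclax start on Day s with no other missed doses.
- Doses available in Days 1 to 28, and days of observation from first venetoclax without extension: 29 - s.
- Days of observation with the extension: 28 (Day s to Day s + 27).
- Days from first venetoclax to Day 42: 43 - s.

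| First venetoclax (s) | Doses in Days 1-28 | Evaluable if DLT-free | Days observed, white-count delay | Days observed, logistical delay | Days to Day 42 |
|---|---|---|---|---|---|
| 1 (no delay) | 28 (100%) | yes | 28 | 28 | 42 |
| 2 | 27 (96.4%) | yes | 27 | 28 | 41 |
| 5 | 24 (85.7%) | yes | 24 | 28 | 38 |
| 8 | 21 (75.0%) | yes | 21 | 28 | 35 |
| 9 | 20 (71.4%) | no, replaced | 20 | 28 | 34 |

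The loss of follow-up among subjects who count is s - 1, so 1 to 7 days. The 75% rule caps it at 7.

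**Conflict inside the existing clause.** A logistically delayed Day 9 starter gets a window to Day 36 (9 + 27). That subject has only 20 of 28 doses in the first 28 days, so is non-evaluable if DLT-free. Adding the white-count delay to the extension, without moving the 75% count, would leave this in place.

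**Direction of the two effects.**
- *Shortened observation (Days 2 to 8).* Clearance probability is (1-q)^6 + 6q(1-q)^5, where q is the DLT probability captured in the window. It rises as q falls, so this effect favours clearance.
- *Replacement (Day 9 on).* Only DLT-free subjects are replaced. The slot's DLT probability is p_short + (1 - p_short) x p_full, which is at least p_full. At equal underlying risk this makes clearance harder.

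**Illustration only.** Assume, without support in the documents, that 21 days capture 75% of the 28-day DLT risk.

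| True DLT rate | Full capture | 2 of 6 delayed 7 days | All 6 delayed 7 days |
|---|---|---|---|
| 0.2 | 0.655 | 0.696 | 0.776 |
| 0.3 | 0.420 | 0.475 | 0.594 |
| 0.4 | 0.233 | 0.287 | 0.420 |

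At a true rate of 0.3 with all six delayed, clearance runs from 0.487 (90% captured) to 0.776 (50% captured). The spread shows how far the size depends on unknowns.

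**The case against.** **The delay may be rare.** Hydroxyurea is allowed before study therapy (inclusion criterion j, Section 5.6.1), and venetoclax is planned from Day 1. If the count is lowered before Day 1, no gap arises. This stands as a limit on size. It does not remove the gap: no white-count ceiling appears among the eligibility criteria, and Section 5.4.1 provides for a count still too high when venetoclax is due.

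**A reader might infer that the missing clause is what allows clearance on 21 of 28 venetoclax doses.** It is not. That floor comes from the 75% rule and applies to everyone. Section 5.4.1 also lets venetoclax stop after the Day 21 marrow, and a Day 1 starter who stops after Day 21 has the same 21/28. The floor would survive the fix. What the clause costs is observation time.

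**A reader might infer that replacing high-count subjects biases the run-in towards clearance.** The arithmetic points the other way. The inference would need a higher DLT risk in the replaced subjects than in their replacements, and the documents say nothing on that.

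**A reader might infer that the haematologic clock also excludes these subjects.** The 42-day sentence can be read either way. If the clock does run from Cycle 1 Day 1, a Day 8 starter reaches Day 42 after 35 days, which would over-call prolonged cytopenia rather than miss it.

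**Safeguards exist.** The last bullet of Section 3.3 already ties SRC review to completed DLT periods, and the SRC sees other safety data. A second six-subject run-in follows at the RP2D, and Bayesian toxicity monitoring follows under Section 9.3. These reduce the consequence. The last two, however, count DLTs under the same definition and so carry the same shortened window.

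**Conclusion.** The gap is real and modest. As written, a Cohort C subject whose venetoclax is deferred to Day 2 to Day 8 for white count counts as a full DLT-free run-in subject with 1 to 7 fewer days of non-haematologic observation on the combination than a subject with an administrative delay of the same length. This leans towards clearance.

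The size cannot be stated from the documents. They do not say how many subjects will have venetoclax deferred after Day 1, for how long, or when DLTs occur, so a claim that most run-ins will be affected is unsupported. From Day 9 the consequence is wasted subjects and, at equal risk, a conservative decision.

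The mismatch between the extension and the period of the 75% count is a separate internal inconsistency that holds whatever the frequency. The result assumes that the 75% rule applies to venetoclax on its own and that no other doses are missed.

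**What to change.** In Section 3.2.2, for Cohort C:
- Run the 28-day DLT window from the first venetoclax dose whatever the reason for a late start, naming the Section 5.4.1 white-count deferral.
- Count the 75% venetoclax requirement over that same window, and say which doses count as planned where it runs past Day 28.
- State whether the 42-day haematologic clock for these subjects runs from Cycle 1 Day 1 or from first venetoclax.
- Keep DLTs countable from the first dose of any study drug.

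In Section 3.3, make the review trigger for the first six subjects the completion of the DLT evaluation period, as its last bullet already implies, and say whether that includes the haematologic clock.

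Cohort D needs no matching change on this ground: Section 5.5.1 starts both treatments together on Day 1, and no mandated deferral of mini-HCVD was found.

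No dose and no white-count rule changes. The run-in review waits by the length of the venetoclax delay in affected subjects, and longer if it is tied to the 42-day clock. No subjects are added, and fewer should need replacing.
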